13.1.2 Collection of overdose and pregnancy

Overdose:

In cases of an overdose (accidental or intentional) with Aubagio® is an event suspected by the Investigator or spontaneously notified by the patient (not based on systematic pills count) and defined as at least twice the intended dose within the intended therapeutic interval.

The circumstances (i.e., accidental or intentional) should be clearly specified in the verbatim and symptoms, if any, entered on separate AE forms. In case of symptomatic overdose, even if not fulfilling a seriousness criterion, is to be reported to the representative of Sanofi within 24 hours of awareness and recorded accordingly on the corresponding pages of the eCRF as explained below. Overdose in the absence of an AE (asymptomatic), is to be reported to the representative of Sanofi within 30 days of awareness. Overdose will be qualified as a SAE only if it fulfils one of the seriousness criteria.

In case of overdose the patient should remain under observation for as long as it is considered appropriate by the Investigator. Appropriate symptomatic measures should be taken.

Pregnancy:

The effect of Aubagio® on human foetal development is not known, and may be potentially harmful based on results from animal studies. Therefore, all patients must be fully informed as to this risk. If during the study, a female patient becomes pregnant or decides to attempt to become pregnant, then she must stop Aubagio® and undergo the accelerated elimination procedure (AEP) (or according to local labeling) [29].

Pregnancy occurring in the patient or the female partner of a male patient included in the study will be reported as an AESI to the representative of Sanofi and recorded within 24 hours of awareness on the corresponding page(s) of the eCRF as explained below.

A pregnancy data collection form will be provided to the Investigator to ensure collection of additional information regarding the outcome of the pregnancy. If the exposed female refuses to provide any information regarding the pregnancy and its outcome, this information will be captured on the Sanofi Pregnancy/Drug Exposure via pregnancy data collection form.

13.1.3 Obligations of the Investigator regarding safety reporting

Adverse Event collection

All AEs, regardless of relationship to Aubagio® spanning from the first dose of Aubagio® after signature of the informed consent until the end of the study as defined by the protocol for each patient, are to be recorded

Property of the Sanofi group - strictly confidential

Version number: Final 2.0

immediately (within 24 hours of awareness) for serious AE and AESI and within 30 days of awareness for non-serious AEs on the corresponding page(s) of the eCRF as explained below. Assessment of causality of the AE to the study drug should be recorded (i.e., related, not related) as well as information about assessment of intensity and outcome of the AEs.

Laboratory and vital signs abnormalities are to be recorded as AEs only if they are medically relevant: symptomatic, requiring corrective treatment, leading to treatment modification (delay, reduction, or discontinuation) and/or fulfilling a seriousness/adverse event of special interest criterion.

Adverse Event reporting to Sanofi

Serious Adverse Events and Adverse Events of Special Interest In the case of an SAE or AESI the Investigator must immediately:

• Enter the information related to the SAE or AESI in the appropriate screens of the eCRF and SEND (within 24 hours of awareness, preferably by email or fax) the signed and dated corresponding page(s) in the Case Report Form to the Sponsor:

E-mail: [contact]

International Toll Free [contact]

Back up Fax 1: [name] Back up Fax 2: [name]

ATTACH the photocopy of all examinations carried out and the dates on which these examinations were
performed. Care should be taken to ensure that the patient's identity is protected and the patient's
identifiers in the study are properly mentioned on any copy of source document provided to for
laboratory results, include the laboratory normal ranges;

All further documentation should be sent to the Sponsor within 24 hours of knowledge. In addition, any effort should be made to further document each SAE that is fatal or life threatening within the week (7 days) following initial notification.

A back-up plan is used (using paper forms) in case the eCRF system does not work.

Non-Serious Adverse Events

In the case of an AE that does not meet the criteria for serious, the Investigator must:

 ENTER (within 30 days of awareness) the information related to the AE in the appropriate screens of the eCRF; and send (within 30 days of awareness) the signed and dated corresponding pages in the eCRF preferably by fax or email to the sponsor:

E-mail: [contact]

International Toll Free [contact]

Back up Fax 1: [name] Back up Fax 2: [name]

A back-up plan is used (using paper forms) in case the eCRF system does not work.

Safety observations

- The Investigator should take all appropriate measures to ensure the safety of the patients as per normal practice.
- The patient must be followed up until clinical recovery is complete and laboratory results have returned to normal, or until progression has been stabilized. This may imply that follow-up will continue after the patient has left the study.
- In case of any SAE brought to the attention of the Investigator at any time after cessation of Aubagio®, and considered by him/her to be caused by Aubagio® with a reasonable possibility, this should be reported to the Sponsor.

13.2 ADVERSE EVENTS OF SPECIAL INTEREST (AESI)

An AESI (serious or non-serious) is one of scientific and medical concern specific to the product, for which ongoing monitoring and rapid communication by the Investigator to the Sponsor or a designated representative is required. Such AEs normally require thorough documentation and investigation to characterize them.

AESIs may be added or removed during a study by protocol amendment.

For AESIs the sponsor will be informed immediately (i.e., within 24 hours), as per the SAE/AESI notification instructions described in Section 13.1.3, even if the AESI does not fulfil a seriousness criterion, using the corresponding screens in the eCRF and reporting the corresponding CRF pages by fax or email.

AESIs

The following events must be systematically reported by the Investigator as AESIs with immediate notification:

- Pregnancy
- Symptomatic overdose with Aubagio®
- Liver disorder with increases in transaminases and bilirubin
 - ALT ≥3ULN (if baseline ALT <ULN); or ALT ≥2 x ALT baseline (if baseline ≥ ULN)
 - Any occurrence of ALT >8 x ULN. This should be reported as SAE with the criteria of medical importance
 - Per the Aubagio® product information [29], discontinuation of Aubagio® therapy is to be considered if elevated liver enzymes (>3 x ULN) are confirmed
- Medically significant neutropenia (any occurrence of neutrophil count of less than 1000 cells/μL)
- Respiratory symptoms compatible with interstitial lung disease (ILD)
- Peripheral neuropathy
- Acute renal failure/ hyperkalaemia
- Medically significant increases in blood pressure (hypertension: SBP ≥160 mmHg AND/OR DBP ≥100 mmHa)
- Severe skin or allergic reaction
- Major depressive disorder and suicidal attempt (based on Investigator's clinical judgment)
- Intense treatment in an emergency room or at home for:
 - Allergic bronchospasm
 - Blood dyscrasias (i.e., agranulocytosis, aplastic anaemia, bone marrow aplasia, myelodysplasia, pancytopenia, etc)
 - Convulsions (Seizures, epilepsy, epileptic fit, absence, etc.)
- Development of drug dependency or drug abuse
- Suicide attempt or any event suggestive of suicidality
- Syncope, loss of consciousness (expect if documented as a consequence of blood sampling)
- Bullous cutaneous eruptions

- Cancers diagnosed during the study or aggravated during the study (only if judged unusual/significant by the investigators)
- Chronic neurodegenerative disease (newly diagnosed) or aggravated during the study (only if judged unusual/significant by the investigators in studies assessing specifically the effect of a study drug on these diseases).

13.3 OBLIGATIONS OF THE SPONSOR

During the course of the study, the Sponsor or the Sponsor's representative will report to the appropriate Health Authorities all cases that meet expedited reporting criteria in accordance with all local and global regulations.

The Sponsor will report all safety observations made during the conduct of the study in the study report.

14 STATISTICAL CONSIDERATIONS

14.1 DETERMINATION OF SAMPLE SIZE The sample size has been calculated in order to assess the primary objective, describe changes in MSIS-29 scores from baseline to month 24. Mean MSIS-29 score on baseline, 24 months and changes during the follow-up (baseline to 24 months) will be calculated with the 95% confidence interval (CI). Taking into account a standard deviation of 20 points in MSIS-29 (Glenn, 2016), a sample size of 100 allows to estimate the MSIS-29 scores with a precision (distance from the mean to the limits of the 95% CI) of about 4 points with a significance level of 0.05. The sample size of 100 patients has been also determined based on the average number of patients at each site within the recruitment period of 2 years.

14.2 ANALYSIS POPULATIONS

The analysis population will include all enrolled patients who received at least one dose of study medication. All study analysis, including safety analysis, will be performed in this population.

14.3 STATISTICAL METHODS

This section provides specifications for preparation of the final SAP, which will be issued prior to database lock. Any differences compared to this statistical section will be identified and documented in the final SAP.

14.3.1 Statistical Analysis

All recorded clinical observations will be analysed using descriptive statistics.

Data will be summarized into counts of non-missing data, mean, standard deviation, and minimum, maximum, median, Q1, and Q3 for quantitative variables and frequency and percent for categorical data. The 95% confidence interval will be provided when necessary.

Subgroup analysis may be conducted as deemed necessary.

14.3.1.1 Primary Analysis

The primary endpoint of change from baseline to month 24 in the MSIS-29 will be analysed descriptively providing the mean change with 95% confidence interval and also using an analysis of covariance (ANCOVA), adjusting for baseline covariates, including the baseline MSIS-29 value. A p-value below 0.05 will be considered statistically significant.

Additional exploratory pre-specified analysis of the primary endpoint will be performed in at least 4 specific subgroups: treatment naïve patients, patients previously treated with a MS DMT within the past 2 years, injectable switch patients and oral switch patients.

14.3.1.2 Secondary Analysis

The changes from baseline to month 24, and to each follow-up visit before 24 months visit, in TSQM v1.4, PDDS, MFIS-5, HRPQ-MS v2, MSISQ-19, SDMT and HADS will be tested using the t-distribution. The mean changes between study visits with the corresponding 95% confidence interval will be given. If required, an ANCOVA, adjusting for baseline covariates will be performed. A p-value below 0.05 will be considered statistically significant. The evolution of PRO scores during the follow-up period will be also represented graphically.

In addition to PRO scores, the same statistical methods will be used to analyse number of missed doses of Aubagio® (adherence), number of relapses, number of HCP encounters and number of emergency room visits.

Additional exploratory pre-specified analysis of the secondary endpoints will be performed in at least 4 specific subgroups: treatment naïve patients, patients previously treated with a MS DMT within the past 2 years, injectable switch patients and oral switch patients.

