2.2 STUDY FLOW CHART

				Core Study		
Visits (V)	V1	V2 (if part of clinical practice)	V3	V4	V5 (if part of clinical practice)	V6/EOS
Months	Baseline ^a	M3 ±1 month	M6 ±1 month	M12 ±1 month	M18 ±1 month	M24 ±1 month
Eligibility (according to SmPC)	Х					
Patient Information / Informed Consent	Х					
Demographics (gender, year of birth, smoking history ^b)	Х					
MS disease history (date of first symptoms, date of diagnosis, number of relapses in the past 2 years, time since last relapse, disability progression / current EDSS)	Х					
Previous DMTs (previous drugs), current drug, time since treatment) $^{\it c}$	Х					
Reason to start/change DMT	Х					
Prior and concomitant medications	Х	Х	Х	Х	Х	Х
Number of relapses since last visit		Х	Х	Х	Х	Х
MSIS-29	Χď		Xi	X ⁱ	Xi	X ⁱ
MFIS-5	χď		X ⁱ	X ⁱ	Xi	X ⁱ
HADS	χď		Xi	Xi	Xi	X ⁱ
SDMT	Χď		Х	Х	Х	Х
MSISQ-19	χď		Xi	X ⁱ	Xi	Xi
TSQM v1.4	Xc,d		X ⁱ	X ⁱ	Xi	X ⁱ
PDDS	X _q		X ⁱ	X ⁱ	Xi	X ⁱ
Treatment adherence to Aubagio (number of missed doses since last visit)		Х	Х	Х	Х	Х
Number of unscheduled and scheduled HCP encounters ^f	Х	Х	Х	Х	Х	Х
Number of emergency visits ^f	Х	Х	Х	Х	Х	Х
HRPQ-MS	X ^d			X ⁱ		Xi
AEs, AESIs, SAEs ^e	Х	Х	Х	Х	Х	Х

- a Baseline visit completed within 4 weeks of first dose of Aubagio[®].
- b Smoking history includes current/former smoker, average consumption, pack years exposure, and time since cessation of smoking (if applicable).
- *c* Patients with previous DMT.
- d Within 4 weeks of first dose of Aubagio[®].
- e AEs (including SAEs & AESIs) within 4 weeks after first dose of Aubagio® will be retrospectively collected upon signing of the informed consent and on an ongoing basis including scheduled visits (eg., patients should report all AEs, SAEs and AESIs during the study period).
- f For baseline this is over the past 12 months
- g Performed in accordance with the local approved SmPC and the Aubagio $^{\circledR}$ RMP
- h In addition to study visits there may be up to 3 monthly telephone calls in order to follow up on potential AEs/AESis/SAEs

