7.2 DURATION OF STUDY PARTICIPATION FOR EACH PATIENT

The duration of the study for each patient will be 2 years (24±1 months). There will be a maximum of 6 study visits for participating patients. Data collection will be at baseline (Visit 1) and at month 3* (Visit 2), month 6 (visit 3), month 12 (visit 4), month 18* (visit 5), and month 24/End of study (EOS).

The baseline visit should occur within 4 weeks of the first dose of Aubagio[®]. All other visits should occur within a time window of ±1 month.

Note that not all study sites will have a month 3 and / or month 18 office visit, according to local practice, but if a month 3 and/ or month 18 visit is performed, data will be collected). Additional visits may occur according to the local clinical practice.

Eligible patients who meet the inclusion and exclusion criteria and sign the informed consent will be enrolled into the study.

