7.3.1 Baseline Visit

The following patient characteristics will be recorded at the baseline visit (completed within 4 weeks of first dose of Aubagio®):

- Patient demographics (gender, year of birth, smoking history)
- MS disease history
 - Date of first symptoms: month and year
 - Date of diagnosis: month and year
 - Number of relapses in the 2 years prior to enrolment
 - Time since last relapse
 - Disability progression/Expanded Disability Status Scale (EDSS) score
- Previous/current treatment with DMTs, if applicable
 - Treatment start and stop dates
 - Reason for starting/changing treatment
- Prior and concomitant medications
- Medical/surgical history and co-morbidities
- PROs (collected within 4 weeks of first dose of Aubagio®):
 - Multiple Sclerosis Impact Scale (MSIS-29) questionnaire
 - Modified Fatique Impact Scale (MFIS-5) questionnaire
 - Hospital Anxiety and Depression (HADS) guestionnaire
 - Symbol Digit Modalities Test
 - Multiple Sclerosis Intimacy and Sexuality (MSISQ-19) Questionnaire
 - Treatment Satisfaction Questionnaire for Medication version 1.4 (TSQM v1.4) questionnaire
 - Patient Determined Disease Steps (PDDS) questionnaire
- Number of scheduled and unscheduled HCP encounters within the past 12 months
- Number of emergency visits in past 12 months
- Health Related Productivity Question-MS (HRPQ-MS) questionnaire
- AEs/SAEs/AESIs since first dose of Aubagio® will be retrospectively collected upon signature of Informed Consent Form

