7.3.2 Visit 2 (Month 3)

The following data will be recorded at visit 2 (month 3), this visit will only occur if part of routine clinical practice:

- Prior and concomitant medications
- Number of relapses since last visit
- Treatment adherence number of missed doses since last visit
- Number of unscheduled and scheduled HCP encounters since last visit
- Number of emergency visits since last visit
- Safety information (AEs/AESIs/SAEs)

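### Relapses, healthcare encounters, emergency visits and missed doses are put under t-tested change from baseline, but their counting windows mostly differ before and after baseline

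*Protocol*

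**What the plan says.** **Method.** Protocol section 14.3.1.2 names the comparisons for the patient-reported scores: "The changes from baseline to month 24, and to each follow-up visit before 24 months visit". These "will be tested using the t-distribution", mean changes between visits are given with 95% confidence intervals, and "A p-value below 0.05 will be considered statistically significant". The next paragraph carries this over: "the same statistical methods will be used to analyse number of missed doses of Aubagio® (adherence), number of relapses, number of HCP encounters", and emergency room visits as well. The synopsis repeats both paragraphs. Neither place mentions a rate, time at risk or a common counting period.

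**Baseline counts.** Section 7.3.1 records "Number of relapses in the 2 years prior to enrolment". For HCP encounters and emergency visits, footnote f of the flow chart (section 2.2) says "For baseline this is over the past 12 months". Missed doses are not collected at baseline.

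**Follow-up counts.** All four items are counted from the previous visit; section 7.3.2, for example, lists "Number of unscheduled and scheduled HCP encounters since last visit". Section 7.3.3 does the same for later visits. The length of that interval varies by site, because "not all study sites will have a month 3 and / or month 18 office visit" (section 7.2).

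**Relapse endpoint.** The synopsis describes relapses counted since baseline. Section 7.4.2 instead refers to relapses at baseline, at each visit and at month 24.

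**The concern.** A change from baseline in a raw count means something only if both counts cover the same length of time. Here the baseline window is usually longer than the follow-up window, so the calculation yields a fall even if nothing has changed. The error has one direction: fewer relapses and less healthcare use after starting the study drug. Section 7.1 states that there is no control group, so nothing in the study would expose it.

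Relapses, adherence and health economic outcomes are stated secondary objectives (section 6.2). An interim analysis for congress presentations is planned 18 months after the first patient enters (section 14.3.3). No patient can have reached month 24 by then. If these counts are included, the scheduled comparisons available would all be earlier ones, where the windows do not match.

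**Working it through.** The protocol gives no expected rate or precision for these counts, so there is no figure of its own to reproduce.

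**Inputs.** Baseline windows: 24 months for relapses, 12 months for HCP encounters and emergency visits, none for missed doses (sections 2.2 and 7.3.1). Visits: months 0, 3 (optional), 6, 12, 18 (optional) and 24 (section 7.2). The nominal time since the last visit is therefore 3 months at month 3; 3 or 6 at month 6; 6 at month 12; 6 at month 18; and 6 or 12 at month 24.

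**Formula.** With a constant rate, expected count = rate × window. The apparent relative change is follow-up window ÷ baseline window − 1. The rate cancels, so these percentages need no assumed rate.

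| Follow-up window | Relapses (24-month baseline) | HCP and emergency visits (12-month baseline) |
|---|---|---|
| 3 months | 3/24 − 1 = −87.5% | 3/12 − 1 = −75% |
| 6 months | 6/24 − 1 = −75% | 6/12 − 1 = −50% |
| 12 months | 12/24 − 1 = −50% | 12/12 − 1 = 0% |

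**Relapses counted cumulatively since baseline (synopsis wording).** Month 3: −87.5%. Month 6: 6/24 − 1 = −75%. Month 12: 12/24 − 1 = −50%. Month 18: 18/24 − 1 = −25%. Month 24: 24/24 − 1 = 0%.

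**Month 24, HCP and emergency visits.** Patients with a month 18 visit show −50% and those without show 0%. The pooled figure falls between these and depends on the mix of sites.

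**Missed doses.** With no baseline value, a change from baseline is undefined. Changes between visits remain possible but carry the same artefact. At an illustrative constant 1 missed dose per month, going from a 3- to a 6-month window adds 6 − 3 = 3, and from a 6- to a 12-month window adds 12 − 6 = 6.

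**How often the t-test would call it significant.** This does need assumptions, because the protocol gives no rates. One-sample t-tests on the change were simulated with 100 patients, 2,000 runs per setting, an unchanged rate and gamma-Poisson counts with frailty variance 0.5.

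| Count (assumed rate per year) | 3-month window | 6-month window | 12-month window |
|---|---|---|---|
| Relapses (0.2 to 1.0) | 100% | 99.4% to 100% | 71% to 100% |
| HCP encounters (2 to 8) | 100% | 100% | 4.8% to 5.4% (matched) |
| Emergency visits (0.1 to 0.5) | 57% to 99.8% | 23.4% to 83% | 4.4% to 4.6% (matched) |

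Relapses over 24 against 24 months gave 4.6% to 4.8%. When counts were first divided by window length, the same t-test rejected in 4.7% to 5.6% of runs over the five settings tried, four of them with unequal windows.

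**What the nominal windows leave out.** Each follow-up visit may move by ±1 month, so a nominal 6-month gap between two of them can run from 4 to 8 months. A patient who stops treatment early has the end-of-study evaluations as soon as possible (section 8.5), which makes the last window patient-specific.

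**The case against.** The strongest reply is that the endpoint lists word these four items as numbers, while the questionnaire scores are worded as changes. The relapse objective is likewise to describe a number over two years. Since no change can be computed for missed doses, the carry-over sentence might mean only t-based means and intervals. That is a possible reading and it limits certainty. But section 14.3.1.2 is the operative instruction, and the only methods it has just described are changes from baseline and between visits. Unequal intervals would distort between-visit changes too.

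A second reply is that annualising counts is ordinary SAP work. This would stand if the protocol were silent. It names a method instead, and section 14.3 presents itself as the specification for the SAP.

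Several stronger conclusions are tempting, but the documents do not support them:

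- A reader might infer that every month 24 result is affected. Windows match for HCP and emergency visits when month 18 is skipped, and for relapses on the cumulative wording.
- A reader might set a 24-month cumulative HCP count against the 12-month baseline and find a doubling. The protocol defines no such cumulative count.
- A reader might expect sites with and without the optional visits to be reported as different. Section 14.3 plans no between-site comparison; the mix only blurs the pooled result.
- A reader might assume that significance is assured. For rare emergency visits it is not.
- A reader might conclude that the t-test must give way to a count model. In the simulated settings, rescaling alone brought the error back to about 5%.

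**Conclusion.** The point holds in limited form. Followed on its plain reading, section 14.3.1.2 and the matching synopsis text turn an unchanged rate into an apparent fall of 50% to 87.5% in per-visit relapse counts, and of 50% to 75% in HCP encounters and emergency visits over 3- or 6-month windows. For missed doses they ask for a quantity that does not exist. On the cumulative reading of relapses, month 24 is sound but earlier visits still compare 3 to 18 months with 24.

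The percentages rest only on the nominal windows and a constant rate. The rejection rates rest on assumed event rates and overdispersion and are illustrative. The primary MSIS-29 endpoint, the sample size and the counts collected are unaffected.

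**What to change.** In the secondary analyses of the synopsis and in section 14.3.1.2, replace the carry-over sentence with a rule for counts:

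- Put each count on a common time base before any comparison: sum the counts since the last visit within the period and divide by the time actually observed.
- Compare HCP encounters and emergency visits in the 12 months before baseline with months 0 to 12 and months 12 to 24.
- Compare relapses in the 24 months before baseline with the 24 months after.
- Report missed doses per unit of time on treatment, with no change from baseline.
- Give the relapse endpoint one wording in the synopsis and section 7.4.2.

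A Poisson or negative binomial model with log observed time as offset is a reasonable option, not a requirement.

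The cost is wording and a little programming, since the counts and visits are already recorded. One item to check is the date of stopping treatment. The follow-up data lists do not itemise it, so confirm that the eCRF captures it as the denominator for missed doses. The change should be in place before the interim analysis.

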6.2 SECONDARY

To describe the change in the following PROs at 2 years, in patients commencing on treatment with Aubagio® in routine clinical practice for RRMS:

- Fatique
- Anxiety and depression
- Cognition
- Sexual dysfunction
- Disease progression
- Treatment satisfaction
- Treatment adherence

To describe the number of relapses during the two year study period in patients commencing on treatment with Aubagio® in routine clinical practice for RRMS

To describe health economic outcomes in patients with RRMS treated with Aubagio® assessed by the number of scheduled and unscheduled healthcare provider (HCP) encounters and emergency visits as well as productivity loss.

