Patient-reported outcomes, clinical outcomes and safety findings during routine clinical practice will be recorded for the entire cohort as well as for defined subgroups (i.e., patients who are treatment naïve, patients who switched from other DMT's). No control group will be included.

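### The p<0.05 change-from-baseline test for relapses uses the 2 years before a treatment start or switch as baseline, with no control group, so selection alone can produce a significant fall

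*Protocol*

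**What the plan says.** Section 14.3.1.2 first sets the method for the questionnaire scores and the SDMT. "The changes from baseline to month 24, and to each follow-up visit before 24 months visit" are tested with the t-distribution, with ANCOVA if required, and "A p-value below 0.05 will be considered statistically significant". The next paragraph extends this: "the same statistical methods will be used to analyse number of missed doses of Aubagio® (adherence), number of relapses, number of HCP encounters" and emergency room visits. The synopsis repeats both paragraphs.

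The baseline values for these counts are look-backs, listed in section 7.3.1:

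- relapses: "Number of relapses in the 2 years prior to enrolment"
- encounters: "Number of scheduled and unscheduled HCP encounters within the past 12 months"
- emergency visits: "Number of emergency visits in past 12 months"

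Section 7.4.2 names a relapse count at baseline alongside the visit counts; the synopsis endpoint counts relapses since baseline. On-study counts are collected since the previous visit, up to month 24 (sections 7.3.2 and 7.3.3).

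Patients enter within 4 weeks of first starting Aubagio, and the reason for starting or changing treatment is recorded (sections 8.2 and 7.3.1). Section 7.1 states "No control group will be included". The relapse objective in section 6.2 is only "To describe the number of relapses during the two year study period".

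**The concern.** A change-from-baseline test needs a baseline, and for relapses the only one collected is the look-back that ends at the treatment decision. Recent disease activity is a plausible reason for such a decision. Patients who enter on a relapse have a look-back count that is high partly by chance, and their later count moves back toward their own long-run rate whatever the drug does.

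Matching the windows does not remove this; for relapses they already match at 24 months each. Without a control group nothing separates this fall from a treatment effect. The protocol attaches a significance rule to the change and states no limit on its reading. Section 14.3.3 says that interim results will go mainly to congress publications and presentations, where a significant fall in relapses could be taken as effectiveness. The descriptive objective does not need the test.

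**Working it through.** **The plan's own figure.** The only calculated figure is for MSIS-29 (section 14.1): half-width 1.96 × 20/√100 = 3.92, which agrees with the stated 4 points or so. No calculation is given for the counts.

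**Inputs from the protocol.** n=100 (section 14.1); p<0.05, taken as two-sided (14.3.1.2); relapse windows 24 months before (7.3.1) and 24 months after (7.2); no relapse required for entry (8.2).

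**Assumptions, because the protocol gives no values.** Each patient has a constant relapse rate before and after (no drug effect), gamma-distributed with mean m = 0.4 to 0.6 per year and shape k = 1 to 4. Counts are Poisson given the rate. A share s of patients enters because of at least one relapse in the prior 2 years; the rest are unselected. Everyone is followed for 24 months.

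**Formulas for the triggered patients.**

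- No relapse in 2 years: P0 = (1 + 2m/k)^(−k)
- Mean before: 2m/(1 − P0)
- Expected later count of a patient with none before: μ0 = 2mk/(k + 2m)
- Mean after: (2m − P0·μ0)/(1 − P0)
- Proportional fall, after simplification: (1 + 2m/k)^(−(k+1))
- Mean squared difference: E1 = [4m − P0(μ0 + μ0²(1 + 1/k))]/(1 − P0)

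Unselected patients have mean difference 0 and mean squared difference 4m. With D the triggered patients' mean after minus mean before, the mixed sample has d = sD, variance sE1 + (1 − s)4m − d², and expected t = 10·d/SD.

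**Worked case, m = 0.4, k = 2, s = 1.** P0 = 1.4^(−2) = 0.510. Before: 0.8/0.490 = 1.63. μ0 = 0.571. After: (0.8 − 0.510 × 0.571)/0.490 = 1.04. Fall: 1.4^(−3) = 36%. E1 = 2.16, SD = √(2.16 − 0.595²) = 1.34, t = −10 × 0.595/1.34 = −4.4.

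**Ends of the range, s = 1.** k = 4, m = 0.4: 1.2^(−5) = 40%, t = −5.0. k = 1, m = 0.6: 2.2^(−2) = 21%, t = −2.5.

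**By share.** The last column is approximately Φ(−1.98 − t), the chance of a significant fall, nominally 2.5%.

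| Share entering on a relapse | Fall in 2-year count | Expected t, n=100 | Chance of a significant fall |
|---|---|---|---|
| 100% | 21–40% | −2.5 to −5.0 | 71–100% |
| 70% | 17–33% | −1.8 to −3.4 | 44–92% |
| 50% | 13–27% | −1.3 to −2.4 | 26–66% |
| 25% | 8–16% | −0.7 to −1.2 | 10–22% |

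**Sensitivity to the trigger.** With a relapse in the last 12 months as trigger, rates of 0.3 to 0.5 per year and shape 1 to 2, simulation at n=100 gives a significant fall in 2–3% (share 0), 18–42% (25%), 51–90% (50%) and 96–100% (100%).

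**Healthcare use, simulated at n=100.** Assumed: 3 background contacts per year plus 2 per relapse; 0.1 emergency visits per year plus 0.2 per relapse; trigger a relapse in the last 12 months; shares 0/25/50/100%.

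- Encounters, equal 12-month windows, no extra contacts: significant fall in 3/15/41/91%.
- Encounters, one extra monitoring contact per year: fall in 0/0/0.3/14%, significant rise in 79/39/13/0.1%.
- Emergency visits, equal windows: fall in 3/6/13/37%.
- Windows as collected, 12 months before against 24 months cumulative: practically no false fall (at most 0.1%); encounters rise significantly in 100%, emergency visits in 25–70%.

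**The case against.** The before/after test is implied, not stated. Missed doses stand in the same sentence and have no baseline value, so the phrase cannot mean change from baseline for every item listed. Encounters and emergency visits are endpoints as plain numbers, while the HRPQ-MS item beside them is worded as a change from baseline. The synopsis counts relapses since baseline. This lowers certainty about what will be run. It does not remove the point for relapses, since section 7.4.2 names a baseline relapse count and section 7.3.1 collects one.

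The absence of a control group is stated openly, the objectives are descriptive, and no passage attributes a change in these counts to Aubagio. That is fair, and misreading by others is a prediction. But the significance rule is fixed in the protocol and goes beyond describing.

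A reader might infer that a significant fall is built in for all three counts. The documents do not support that. Entry requires no relapse, and the distribution of reasons for starting is not given; at a 25% share under the 2-year trigger, the expected t is well short of significance. For encounters and emergency visits, the laboratory monitoring in section 7.3.3 may add contacts and the unequal windows push counts up, so no fall can be presumed.

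**Conclusion.** The point holds for relapses in conditional form. If section 14.3.1.2 is followed with the look-back as baseline, a fall can be expected to the extent that patients start because of recent relapses, and it cannot be told apart from a drug effect. Its size runs from negligible with no relapse-driven entry to a 21–40% fall, significant in most replications, if all enter that way under the 2-year trigger. Rate, spread, trigger and share are all assumptions; the protocol supplies none of them. For encounters and emergency visits the direction is uncertain, and the conclusion is only that an uncontrolled before/after p-value is no more interpretable there. These are secondary outcomes; the primary analysis is not affected by this point.

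**What to change.** In section 14.3.1.2 and the matching synopsis text:

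- Take relapses, encounters and emergency visits out of the change-from-baseline significance test.
- Report the on-study number and the rate per patient-year with a 95% CI. Section 6.2 asks only for numbers; the rate is added because section 8.5 brings the final evaluations forward when treatment stops early, so observation times will differ.
- If a before/after contrast is shown, present it descriptively without a p-value, and state that a fall in relapses can be expected from selection.

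The cost is wording and table layouts, with no new data. The sponsor gives up a before/after p-value.
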